## BACKGROUND & PROJECT SUMMARY

Electronic cigarettes (e-cigarettes) have a potential role in smoking cessation and harm reduction for tobacco cigarette smokers. As of 2019, the most popular e-cigarette is JUUL, a pod type device containing e-liquids with high nicotine content. The goal of this study is to better understand the pharmacokinetic and pharmacodynamics responses produced by the JUUL e-cigarette, compared to tobacco cigarettes, in e-cigarette and tobacco cigarette smokers.

## 2 RESEARCH AIMS

### 2.1 SPECIFIC AIM #1

To categorize the nicotine PK profile (maximum plasma concentration; time to maximum plasma concentration and area under the concentration-time curve) and compare when using the JUUL e-cigarette vs. a tobacco cigarette in a standardized manner.

### 2.2 SPECIFIC AIM #2

To categorize the nicotine PK profile (maximum plasma concentration; time to maximum plasma concentration and area under the concentration-time curve) and compare when using the JUUL e-cigarette vs a tobacco cigarette when using the product ad libitum.

### 2.3 SPECIFIC AIM #3

To evaluate various outcomes following JUUL e-cigarette or tobacco cigarette use, both with standardized and ad lib use including: heart rate, plasma catecholamines, pulmonary function testing.

### 2.4 SPECIFIC AIM #4

To evaluate and compare the effects on craving, reward and satisfaction when using the JUUL e-cigarette vs. tobacco cigarette.

## 3 STUDY DESIGN

### 3.1 DESIGN SUMMARY

This is an observational, crossover design that will examine the pharmacokinetics and pharmacodynamics of impact of smoking tobacco cigarettes or vaping the JUUL electronic cigarette. Participants will be recruited in two groups: primary e-cigarette vapers and primary cigarette smokers. The order of assignment to either tobacco cigarettes or the JUUL electronic cigarette will be counter-balanced via a latin square design.

### 3.2 ENROLLMENT TARGET

We will enroll a total of 30 participants, across two groups; 15 primary cigarette smokers who may have occasionally used electronic cigarettes and 15 experienced electronic cigarette users who occasionally smoke tobacco cigarettes. We will seek to enroll equal numbers in each group, but will remain flexible during recruitment.

### 3.3 STUDY TIMELINE

1. Preparation for this study began in May 2019
2. Application submitted to the UCSF IRB: July 2019

3. UCSF IRB Initial Approval date: September, 2019
4. Estimated start date: September 2019
5. Estimated end date: September 2023

### 3.4 ELIGIBILITY

All individuals interested in participating and who meet the inclusion/exclusion criteria will be invited to be part of the study. Inclusion criteria are described below.

#### 3.4.1 Inclusion Criteria

- Healthy on the basis of medical history and limited physical examination, as described below:
  - Heart rate < 105 BPM\*
  - Systolic Blood Pressure < 160 and > 90\*
  - Diastolic Blood Pressure < 100 and > 50\*
- \**Considered out of range if both machine and manual readings are above/below these thresholds.*
- Age:  $\geq 21$  &  $\leq 70$  years old
- Body Mass Index  $\leq 38.0$  (*at PI's discretion for higher BMI if no other concurrent health issues*)
- Willingness to avoid combusted marijuana up to 48 hours before each study visit
- Willingness to the avoid use of any non-legally sourced cannabis product for the duration of the study
- Nicotine strength of e-liquid of usual e-cigarette  $> 0$  mg/ml
- **Group 1 Experienced E-cigarette users**
  - Current use of tobacco cigarettes ( $< 5$  cigarettes per day)
  - Current e-cigarette use at least 15 days out of the past 30 days of a non-mod e-cigarette
- **Group 2 Primary Tobacco cigarette users:**
  - Currently smoking  $\geq 5$  cigarettes per day
  - Current e-cigarette use must be  $< 5$  times per month
- Saliva cotinine  $\geq 50$  ng/ml or urine cotinine and/or NicAlert=6
- Must have a smart phone, computer, or tablet and internet access (for remote procedures)

#### 3.4.2 Exclusion Criteria

- Medical
  - Heart disease
  - Seizures
  - Cancer

- Thyroid disease (okay if controlled with medication)
  - Diabetes
  - Hepatitis B or C or Liver disease
  - Glaucoma
  - Kidney disease or urinary retention
  - History of stroke
  - An ulcer in the past year
  - Active use of an inhaler for Asthma or COPD
- Psychiatric conditions
  - Current or past schizophrenia, and/or current or past bipolar disorder
  - Major depression, current or within the past year
  - Major personality disorder
  - Participants with current or past minor or moderate depression and/or anxiety disorders will be reviewed by the PI and/or medical monitor and considered for inclusion
  - History of psychiatric hospitalizations are not exclusionary, but study participation will be determined as per PI's or medical monitor's approval
- Drug/Alcohol Dependence
  - Alcohol or illicit drug dependence within the past 12 months (currently in treatment) with the exception of those who have recently completed an alcohol/drug treatment program
  - Positive toxicology test for illicit drugs at the screening visit (THC & prescribed medications okay)
  - Opioid replacement therapy (including methadone, buprenorphine, or other)
- Psychiatric medications
  - Current regular use of any psychiatric medications is exclusionary, with the exception of SSRIs and SNRIs and current evaluation by the PI and/or medical monitor that the participant is otherwise healthy, stable, and able to participate
- Medications
  - Use of sympatholytic medications for cardiovascular conditions including hypertension (Example: beta and alpha-blockers)
  - Use of medications that are inducers of nicotine metabolizing enzyme CYP2A6 (Example: rifampicin, carbamazepine, phenobarbital, and other anticonvulsant drugs)
  - Concurrent use of nicotine-containing medications

- Any stimulant medications (example: Adderall) generally given for ADHD treatment
- Use of Other Tobacco Products (OTP)
  - Any of the following products in combination more than 15 times in the past month
  - smokeless tobacco (snus, oral snuff, chewing tobacco)
  - pipes
  - cigars, cigarillos, little cigars
  - blunts, spliffs
  - hookah
- Other/Misc. Chronic Health Conditions
- Fainting (within the last 30 days)
- Other “life threatening illnesses” as per PI’s or medical monitor’s discretion
- Pregnancy
  - Pregnancy (self-reported and urine pregnancy test)
  - Breastfeeding (determined by self-report)
- Concurrent participation in another clinical trial (at PI’s discretion)
- Inability to read and write in English
- Planning to quit smoking or vaping within the next 60 days
- Recent onset or change (worsening) in cough, fever and/or abdominal symptoms (vomiting or pain) in the past two weeks
- Diagnosis of pneumonia in the past 3 months
- Uncomfortable with blood draws
- Known allergy to propylene glycol or vegetable glycerin

### **3.4.3 Eligibility Determination**

Eligibility will begin to be determined via a preliminary REDCap online survey. At that time, the CRC will begin an eligibility checklist. The online survey will be followed-up by a phone screen to clarify eligibility questions and the eligibility checklist will be updated. Final eligibility criteria will be evaluated via assessments at the in person screening visit, and saliva cotinine. If the participant is not taking any medications and has no active psychiatric symptoms, the CRC can sign off on the eligibility checklist. Otherwise, the PI and/or Medical Monitor are required to review the participant’s chart and sign off on eligibility.

### **3.4.4 Reassessment of Eligibility**

If there is a positive illicit drug tox at screening, participants will be given 2-weeks to come back and re-screen. In that case, all screening visit procedures are repeated.

Additionally, if their 5B Day 1 visit is set to occur 30-90 days past the date of their screening visit, participants will be asked over the phone by the CRC if they had any recent changes in medications, medical care or tobacco/nicotine use to confirm continued eligibility. If the participant's 5B admissions are more than 90 days past the screening visit, the participant will have to be re-screened.

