## 4 STUDY VISITS & WINDOWS

The chart below describes assessment time points and the desired window between visits. The window will remain flexible to accommodate participants' schedules, and to the discretion of the PI if it is deviated from.

Assessment Time Points	Desired Window
REDCap survey	N/A
Phone Screen	N/A
Screening Visit	Within 30 days of Redcap survey
Orientation	Within 90 days of Screening Visit
5B Hospital Study Day 1	24-32 hours after Orientation Visit (morning admission)
5B Hospital Study Day 2	24 hours- 1-week after H-SD1 (morning admission)

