#### **6.2.4 Urine Collection**

Approximately 150 mL of urine will be collected for a drug toxicology and pregnancy test (females only). If positive for illicit drugs without a valid prescription, the participant will be dismissed without payment. If positive for pregnancy, the participant will be dismissed and paid for the visit. The “Urine Toxicology Screen SOP” and “Pregnancy Screen SOP” are references for these testing processes.

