### 6.3 ORIENTATION

After eligibility is determined, an Orientation visit will be conducted via Zoom. The orientation visit should be at least 24 hours before the first 5B study day. For example, if a participant was oriented on Monday at 12 noon, they should be booked to begin 5B visit on Wednesday morning. This is to ensure they have at least 1 full day to try the JUUL product.

At the remote orientation visit, the following will occur:

- The CRC will review with the participant 5B location, procedures and reminders to not use combusted marijuana and to not smoke from 10PM the night before their 5B admission
- Participants will watch a training video on JUUL
- Participants will be given two flavors to choose from (menthol and tobacco)
- Participants will collect approximately 150 mL of urine. This will be done at home right after the Zoom visit is complete. This will serve as Baseline total nicotine equivalents as a measure of usual daily intake of nicotine.
- Participants will conduct a “curb-side pick-up/drop off” their urine to be aliquoted into two 20mL vials; one vial pH adjusted.
- They will be given their own JUUL device and selected pods (1-2) to use for one whole day before the 5B admission. This will be done within the same day as the Zoom visit, the day before their 5B admission.
- If CTSI CRS is available during the orientation, participant and CRC will go to 5B for nurses to conduct a quick vein check. This is for the nurses to inspect the participant's veins and ensure a successful access the morning of the study.
- Participants will be randomized, using a Latin square design, to distinguish which ARM the participant will start off first for Hospital Study Day 1.

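### The only scheduled pregnancy test is at screening and the reassessment call does not name pregnancy, so the result can be about 90 days old when the study supplies JUUL

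*Protocol*

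**What the plan says.** Section 3.4.2 of the protocol lists as an exclusion "Pregnancy (self-reported and urine pregnancy test"), and breastfeeding by self-report. The test is placed at the in-person screening visit. Section 6.2.4 reads "Approximately 150 mL of urine will be collected for a drug toxicology and pregnancy test (females only"), and sends a woman with a positive result home, paid for the visit.

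Section 3.4.4 sets out what happens when time passes after screening. The trigger is "if their 5B Day 1 visit is set to occur 30-90 days past the date of their screening visit", and then "participants will be asked over the phone by the CRC if they had any recent changes in medications, medical care or tobacco/nicotine use". Beyond 90 days the participant is re-screened. For a Day 1 less than 30 days after screening, nothing is specified.

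The window for orientation in section 4 is "Within 90 days of Screening Visit". Day 1 follows 24 to 32 hours later, and Day 2 between 24 hours and one week after Day 1. At orientation (section 6.3) participants collect about 150 mL of urine at home for baseline nicotine equivalents and drop off "their urine to be aliquoted into two 20mL vials; one vial pH adjusted". The same day they receive a JUUL and pods to use at home before admission.

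Two other exclusions in section 3.4.2 are tied to a time span: "Planning to quit smoking or vaping within the next 60 days", and fainting in the preceding 30 days.

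**The concern.** Section 3.4.4 exists to confirm that a participant is still eligible, so the protocol accepts that eligibility can lapse between screening and exposure. Pregnancy can change within that interval, and the protocol requires a test as well as self-report to rule it out. Yet the recheck omits it by name and repeats no test. A participant who became pregnant after screening could therefore be supplied with a nicotine product by the study, against the protocol's own exclusion, without any departure from the written procedures.

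This concerns a real part of the sample. The SAP (Targeted Population) seeks equal numbers of men and women, which is 15 of 30. Its stated minimum is 25% women, given there as about 5, although 25% of 30 is 7.5. The age range is 21 to 70, so not all of these women could become pregnant. The documents give no pregnancy rate, and none is assumed here.

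**Working it through.** The plan states no figure of its own to reproduce. The check adds up the visit windows and then looks at each contact after screening for anything that would refresh the pregnancy result. Day 0 is the in-person screening visit, and a month is taken as 30.44 days.

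**Age of the test**

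- At Day 1, the longest interval without re-screening is 90 days: 90 / 30.44 = 2.96 months.
- At JUUL handover, with Day 1 on day 90 and orientation 24 to 32 hours before it: 90 − 24/24 = 89 days, or 90 − 32/24 = 88.7 days. The worked example in section 6.3 (Monday noon to Wednesday morning, 44 hours if admission is at 8 AM) gives 90 − 44/24 = 88.2 days.
- At Day 2, the answer depends on how section 3.4.4 is read. Its re-screening rule speaks of admissions in the plural. If both hospital days count, the maximum stays at 90 days. If only Day 1 counts, it is 90 + 7 = 97 days (3.2 months).
- With Day 1 before day 30, the result can be up to 29 days old with no call specified.

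**What each later contact covers**

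| Contact | Stated content | Refreshes the pregnancy result? |
|---|---|---|
| COVID-19 questions before in-person visits (6.1) | Symptoms, contacts, recent positive test | No |
| Call at 30–90 days (3.4.4) | Changes in medicines, care received, nicotine or tobacco habits | Not by name; a known pregnancy under care might come out |
| Orientation urine (6.3) | Nicotine equivalents | No |
| Hospital baseline urine (6.5) | Nicotine equivalents and VOCs | No |
| Medical Monitor's history and examination at admission (7) | Content not given; not listed in 6.5 or 6.6 | Unknown, and after handover |
| Immediate analysis of urine pregnancy test (SAP, Data Acquisition and Transmission) | Retest if needed; no visit named | Not shown |

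**Other time-limited exclusions.** The quit-plan criterion looks 60 days ahead. If it is asked at screening, a Day 1 on day 90 lies 90 − 60 = 30 days past that horizon, so the answer has lapsed for any Day 1 on days 61 to 90. The documents do not say where the question is asked. If it is asked only in the REDCap survey (an assumption), the answer can be 30 + 90 = 120 days old at Day 1. The 30-day fainting criterion is not re-asked in any listed procedure.

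**Window mismatch.** Section 4 allows orientation on day 90. Day 1 then falls on day 90 + 24/24 = 91 to 90 + 32/24 = 91.3, or 90 + 44/24 = 91.8 on the example in section 6.3. Section 3.4.4 requires re-screening beyond day 90.

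**Urine available at orientation.** 150 − 2 × 20 = about 110 mL remains after the two vials. Section 6.3 gives it no stated use.

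**The case against.** The strongest reply is that other safeguards exist. Section 7 gives the Medical Monitor a history and examination at admission, and the screening Medical History form (section 6.2.2) covers exclusionary conditions, so a similar history at admission could well ask about pregnancy. This stands to the extent that a reader should not infer that the phone call is the only recheck. It does not close the gap. The content of that history is not stated, the hospital-day procedures do not list it, and it comes after the participant has had the JUUL at home. The SAP's mention of retesting names no visit, and its context is missing data and sample volume.

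A reader might also take 97 days as the firm maximum. The documents do not support that: the plural in section 3.4.4 more naturally covers both hospital days, which holds the figure at 90.

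A reader might treat the lapsed quit horizon as a second safety gap. That is not supported either. Every participant already uses nicotine, the criterion is written for enrolment, and the plan does not say that the 60 days run from Day 1. The call's question on changed use would also reveal a quit attempt already begun, though not a plan.

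Nor does the mismatch between sections 3.4.4 and 4 show that devices will routinely be issued after the limit. It amounts to a day or two in windows described as desired and flexible, and the date of Day 1 is known when orientation is booked.

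Finally, the Pregnancy Screen SOP is not among the documents reviewed and might set its own repeat timing. That is a fair reservation, carried into the verdict.

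**Conclusion.** The point holds for pregnancy. The visit procedures schedule one test, at screening or re-screening. The reassessment call does not name pregnancy, and nothing is specified below 30 days. The result can be 88 to 89 days old when the JUUL is handed over and 90 days old at Day 1. It reaches 97 days at Day 2 only if the 90-day limit is counted to Day 1 alone.

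These are the longest intervals the windows allow. The documents give no expected interval, so the typical gap may be much shorter. The conclusion assumes that the Pregnancy Screen SOP and the admission history contain no repeat check that the protocol leaves unstated.

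The quit-plan and fainting criteria are a secondary matter of keeping eligibility current. The one-to-two-day mismatch between sections 3.4.4 and 4 is a wording point. None of this affects the power calculation or the analysis. It is a participant-protection gap that should be closed, and closing it needs no new visit or sample.

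**What to change.** 1. In section 6.3, add a step that runs the existing Pregnancy Screen SOP for female participants on the urine dropped off at orientation, before the JUUL is released. If the SOP already requires a repeat test, cite it there.
2. Add pregnancy and breastfeeding to the reassessment questions in section 3.4.4, and ask them of everyone at orientation, whatever the interval since screening.
3. In the same script, re-ask the other time-limited exclusions: plans to quit within 60 days and fainting within 30 days.
4. Reconcile sections 3.4.4 and 4 so that the 90-day limit is counted to the same visit, and say whether it covers Day 2.
5. Reconcile section 7 with sections 6.5 and 6.6 by stating what the admission history and examination cover.

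The cost is one urine test per female participant on a sample already collected, a few scripted questions and some edits to the text. The practical burden lies in the curb-side exchange: staff must run the test, disclose the result privately and hold the device until it is known. An occasional participant will be excluded late, after screening effort has been spent.

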## 4 STUDY VISITS & WINDOWS

The chart below describes assessment time points and the desired window between visits. The window will remain flexible to accommodate participants' schedules, and to the discretion of the PI if it is deviated from.

Assessment Time Points	Desired Window
REDCap survey	N/A
Phone Screen	N/A
Screening Visit	Within 30 days of Redcap survey
Orientation	Within 90 days of Screening Visit
5B Hospital Study Day 1	24-32 hours after Orientation Visit (morning admission)
5B Hospital Study Day 2	24 hours- 1-week after H-SD1 (morning admission)

## 5 STUDY IDS

Study IDs will first be assigned at the time of the REDCap online survey. This ID will start with "TRC" to represent "Tobacco Research Center". This ID will be placed on the eligibility checklist. At the time of consent, a study ID will be assigned beginning with the four digit 5B study research number and followed sequentially starting with 001. For example, the first person consented into the study will be given the ID, 8223-001. This ID will be added to the eligibility checklist and a screening log in Excel will store this ID.

## 6 STUDY PROCEDURES & VISITS

### 6.1 COVID-19 Screening

Prior to booking any participant for **any** in-person visit, we will ask the following screening questions via Zoom or on the phone. The answer must be "NO" to all of them; otherwise, they will need to be rescheduled.

1. Have you had any of the following symptoms in the past 24 hours?
  - Fever (temp >37.8 C or 100 F)
  - Night sweats
  - Shaking/chills
  - Shortness of breath

- Cough
- Sore throat
- Body aches
- Loss of sense of smell or taste

2. In the past 14 days, have you had unprotected close contact (within 6 ft for more than 15 minutes at a time) with someone you know to be diagnosed with COVID-19?  
*(We understand there may be situations in the community in which you may not know the status of strangers. Please answer to your best knowledge for those you do know, such as those with who have frequent contact)*
3. Have you recently tested positive for COVID-19?

## 6.2 SCREENING VISIT

The schedule of procedures for the screening visit will occur across two visits. One will be a **remote visit via Zoom** and the other will be an **in-person visit**.

The following will occur prior or during **the remote visit**:

### 6.2.1 Consent Process

Upon booking the Screening Visit, CRC will initiate the Informed Consent process over the phone. The CRC will first determine interest and then send the participant the informed consent and PowerPoint to their email for their review. When the participant has had time to review, the CRC will utilize the phone script to engage in the consent discussion, reviewing the purpose, procedures, alternatives, benefits, risks and opportunity to ask questions. The CRC will also assess understanding by asking the participant to respond to questions about the study. This process will be documented on the informed consent documentation checklist.

If the participant would still like to be in the study, the CRC will explain that they do need the HIPPA form signed and will do that when the participant comes in for their in-person visit.

The consent form will be sent to the participant via DocuSign. Upon receiving e-signature from the participant, the CRC will sign the consent form.

The participant will be sent a REDCap survey link 24 hours before their remote visit and asked to complete questionnaires included in the Screening Packet before the remote visit is conducted.

At the remote visit, the CRC will first take time to answer any questions about the study that the participant may have.

### **6.2.2 Screening Packet**

Participants will complete the following via their CRC during the remote visit or through the direct Electronic Data Capture (EDC) system. The personal data form and medical history will not be entered into the Electronic Data Capture (EDC) system, but remain source documents.

#### **Personal Data Form [paper source]**

- This section contains the participant's contact information as well as an Emergency Contact.

